GCP	Good Clinical Practice
GGT	Gamma-glutamyl transferase
HIPAA	Health Insurance Portability and Accountability Act of 1996
ICF	Informed consent form
ICH	International Conference on Harmonization
IEC	Independent Ethics Committee
IGA	Investigator Global Assessment
IRB	Institutional Review Board
IUD	Intrauterine device
PGWB	Psychological General Well-Being scale
PI	Principal Investigator
PK	Pharmacokinetic
QoL	Quality of life
SAE	Serious adverse experience
WPAI	Work Productivity and Activity Impairment scale

PROTOCOL SYNOPSIS

TITLE	The impact of dupilumab on quality of life in moderate to severe atopic dermatitis patients
SPONSOR	[name]
FUNDING	Regeneron Pharmaceuticals and Sanofi
STUDY DESIGN & OVERVIEW	This is an open-label study which will examine the effect of dupilumab on quality of life in a real-world setting
PRIMARY OBJECTIVE	To evaluate the improvement in patient quality of life after 52 weeks of treatment with dupilumab using validated dermatologic and non-dermatologic psychometric instruments. The primary endpoint is the improvement in quality of life measured by change in Psychological General Well-Being scale (PGWB) at Week 16 from baseline.
SECONDARY OBJECTIVES	To evaluate physical parameters and patient reported symptoms and satisfaction with treatment after 52 weeks of dupilumab using validated dermatologic and non-dermatologic instruments.
NUMBER OF SUBJECTS	Up to 30 patients will be enrolled
SUBJECT SELECTION CRITERIA	
Inclusion Criteria:
 
 1. Ability to provide written informed consent and comply with the protocol 2. At least 18 years of age 3. Diagnosis of atopic dermatitis at least 6 months prior to enrollment, having stable (unchanged) disease for at least 2 months 4. Non-immune-compromised status 5. Subjects have moderate-to-severe atopic dermatitis, classified as Eczema Area and Severity Index (EASI) score greater than or equal to 6 6. Subject is considered a candidate for phototherapy or systemic therapy 7. Subjects of child-bearing potential must have a negative urine pregnancy test within 7 days prior to first dose of dupilumab 8. Sexually active subjects of childbearing potential must agree to use medically acceptable form of contraception during screening and throughout the study 9. Subject meets concomitant medication requirements (see below) 
Exclusion Criteria:

	
 1. Younger than 18 years of age 2. Has mild atopic dermatitis, classified as EASI score less than 6 3. History of known or suspected intolerance to any of the ingredients of the investigational study product 4. Evidence of skin conditions other than atopic dermatitis that would interfere with study-related evaluations of atopic dermatitis. 5. History of immune-compromised status [e.g. human immunodeficiency virus (HIV) positive status or other immune suppressing drug] or a congenital or acquired immunodeficiency 6. Has a poorly controlled medical condition including, but not limited to, unstable cardiovascular disease, poorly controlled diabetes, recent stroke, history of recurrent infections, or any other condition for which, in the opinion of the investigator, participation in the study would place the subject at risk 7. Has a history of or ongoing drug or alcohol abuse 8. Is not willing to comply with concomitant medication requirements 9. Is known, or suspected of being unable to comply with the study protocol 10. Subjects who are well controlled on current treatment for atopic dermatitis and participation in the study may worsen disease control significantly 11. Subjects who have been previously treated and/or are currently on dupilumab will not be eligible to participate.
STUDY TREATMENT	Dupilumab (Dupixent ®) 600 mg SC at week 0, then 300 mg SC every other week.
STUDY DURATION	The total duration of the study is expected to be 104 weeks: 52 weeks for recruitment and 52 weeks for site visits.
PRIMARY ENDPOINT	Improvement in quality of life measured by change in Psychological General Well-Being scale (PGWB) at Week 16 from baseline.
SECONDARY ENDPOINT	
 1. Improvement in work productivity measured by change in Work Productivity and Activity Impairment scale (WPAI) at Week 16 from baseline 2. Improvement in quality of life measured by change in Dermatology Life Quality Index (DLQI) at Week 16 from baseline 3. Efficacy of drug as measured by EASI and IGA at week 16 from baseline 4. Safety of drug 5. Improvement in itch and pain scores using numerical rating scales at Week 16 from baseline 6. Improvement in sleep quality measured by the Pittsburgh Sleep Quality Assessment (PSQI) at Week 16 from baseline

	7. Evaluation of subjective video documentation
SAFETY EVALUATIONS	Safety will be evaluated by tabulation of adverse events (AEs), including any Serious Adverse Events (SAEs) within treatment groups. All AEs occurring during the study will be recorded. Descriptions of adverse events will include the date of onset, the date the adverse event ended, the severity of the adverse event, and the outcome. All reported adverse events will be summarized by the number of subjects reporting adverse events, body system, severity, seriousness, and relationship to study treatment.
STATISTICS Primary Analysis Plan	The primary endpoint is improvement of PGWB at week 16 compared to baseline. Statistical significance will be based on resulting p-values of 0.05 or less. Last observation carried forward (LOCF) will be used to impute missing data. Analyses will be conducted on an intent-to-treat (ITT) population (all subjects enrolled and receiving the treatments). Analyses on the per-protocol (PP) population will be considered supportive of the ITT analyses. Subjects will be eligible for the PP analyses if they complete the 52 week evaluation without any noteworthy study protocol violations (i.e. failure to use the study medications or investigator activity that could have possibly interfered with the therapeutic administration of the treatment or the precise evaluation of treatment efficacy).
ETHICAL CONSIDERATIONS	This study will be conducted in accordance with applicable laws and regulations and according to the recommendations of International Conference on Harmonization Good Clinical Practice (ICH GCP) guidelines and those of the Declaration of Helsinki (Edinburgh, 2000); only after approval for the study has been obtained from the relevant regulatory authority and relevant independent ethics committee (IEC). The institutional review board (IRB)/IEC must review and approve the protocol and informed consent form (ICF) before any subjects are enrolled. The subject must be consented using the approved ICF before any procedures specified in the protocol are performed.

1 BACKGROUND

Atopic dermatitis (AD) is a common, complex, immune-mediated condition affecting 5-15% of children and adults worldwide. Adults with AD suffer from severe pruritus and inflammatory skin rash with a chronic disease course.

Patients with moderate-to-severe AD report a multidimensional burden including itch, pain, sleep disturbance, anxiety and depression, and impaired health-related quality-of-life (HRQoL). Patients suffering from AD are more likely to be depressed when compared to the general population, which can lead to increased suicidal ideation. Furthermore, AD can create a negative impact in the workplace, as patients with the disease are more likely to miss work due to their skin symptoms. With the significant negative psychosocial impact of AD, patients not only want to improve their skin lesions, but also their personal experience with this chronic disease.

2 STUDY RATIONALE

The overall aim of this study is to demonstrate, beyond the Dermatology Life Quality Index (DLQI), improvement in the quality of life of adults with moderate-to-severe AD who are being treated with dupilumab for 1 year.

The University of California, San Francisco (UCSF) Skin Treatment Center is a high-volume atopic dermatitis referral center whose activities include outpatient care, a phototherapy unit, a Goeckerman tar treatment program, and over 20 clinical trials conducted over the past three years.

The Skin Treatment Center has conducted several similar studies in the treatment of moderate to severe plaque psoriasis, a disease which has taken more than 10 years to be seen as a respectable condition on par with other serious medical diagnoses. In the process of making psoriasis worthy of reimbursement from payers, the government, and even in the eyes of the general public, some key data attesting quantitatively the negative impact of the disease, played a very important role. Having been involved in this process, and learning from the psoriasis experience, our aim is to make atopic dermatitis as respectable as psoriasis, without spending upwards of 10 years to get to that point. The most critical data that can help AD attain this respected status is the quantitative documentation regarding the negative impact of the disease on patients that is comparable to other serious disorders. This cannot be done with the DLQI or any other skin specific instruments.

We have specifically chosen the Psychological General Well Being Index (PGWB) and Work Productivity and Activity Index (WPAI) as quality of life assessment tools because they are *not* specific to skin diseases; they have been used extensively for non-dermatologic serious medical conditions. By deliberately using validated QOL instruments applicable broadly to serious medical conditions, we hope to show that patients being considered for treatment have baseline deficiencies in psychological well-being and work productivity comparable to patients with

serious non-dermatological disorders (such as heart disease, cancer, and untreated diabetes). Moreover, we aim to go beyond this by involving a therapeutic intervention to hopefully show that treatment with dupilumab not only significantly improves these parameters, but also brings them to a level comparable to a disease-free non-patient population.

Beyond administering these questionnaires, we will also take a novel approach to assessing patient experience with a medication. Each patient will be given a video recording device to document their experience from a pre-dupilumab state to a post-dupilumab state in the privacy of their own home. Human-interest stories excite payers and the general public who are not healthcare providers. It is best to have both human-interest stories in a narrative form before and after treatment as well as quantitative documentation with the PGWB and WPAI.

It is hoped that the information gained from this study will not only provide more insight into the psychosocial and occupational impact of AD, but also confirm the value of dermatological care by demonstrating and documenting how an effective treatment modality like dupilumab can reverse these negative impacts.

Thus, in this real-world study of atopic dermatitis, we aim to examine the value and efficacy of medical intervention, extending beyond physical improvement, and into the realm of psychosocial and occupational functions.

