9.1.11 Video recording

Patients will be given a video recording device at week 0, and will be instructed on how to use it to record video. Patients will be instructed to record videos of themselves at home discussing their experience with the study drug and its impact on their skin and quality of life for roughly 5-10 minutes/week. The patient will be the only person in the video (i.e. there will be no family members or others interviewing or participating in the video). The patient will be encouraged to

record in a private setting (i.e. alone in their bedroom or office) and similarly, will be instructed to keep the recording device and its stored footage in a private location. Patients will be given a list of topics at the week 0 visit to be used as guidelines for discussion:

- 1) Please discuss any changes you have observed in your skin while using the study drug.
- 2) What is the most important change that you have experienced while using the study drug?
- 3) What are your goals with undergoing this medication for the future?
- 4) Please discuss how these changes in your skin have impacted both your life (day-to-day behaviors such as clothing choice or activities) and the lives of your loved ones.
- 5) Please discuss any changes in how you feel since starting the study medication (mood, sleep, work, home life, personal relationships).
- 6) Please discuss your overall experience using the study drug.
- 7) Please discuss any interesting or notable experiences or events that have occurred to you while using the study drug.
- 8) Please feel free to discuss anything else pertaining to your experience with eczema

Patients will be instructed to bring in their video recording devices to their study visits at weeks 4, 8, 12, 16, 20, 24, 28, 32, 36, 40, 44, 48, 52, and at early termination when applicable. At these visits, study staff will download the patient videos to a secure local storage site.

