10.02 Visit 2 (Week 0)

1. Review inclusion and exclusion criteria
2. Brief interim medical history
3. Review concomitant medications
4. Physical examination
 - a. Height and weight
 - b. Vital signs: temperature, blood pressure, pulse, and respiratory rate
 - c. Eczema Area and Severity Index (EASI)
 - d. Investigator's Global Assessment (IGA)
5. Urine pregnancy test (if applicable)
6. Full-body photography (excluding face)
7. Quality of Life Measures:
 - a. WPAI
 - b. PGWB
 - c. DLQI

8. Other patient questionnaires:
 - a. Itch Numerical Rating Scale
 - b. Pain Numerical Rating Scale
 - c. Pittsburgh Sleep Quality Assessment (PSQI)
9. Study drug injection
10. Dispense study medication and dosing diaries for home use
11. Sign out video recording device and instruct patients on proper use

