14.2 Analysis of Secondary Endpoints

1. Efficacy Endpoints

- a.** EASI and IGA scores at week 16 will be compared to baseline.

2. Safety Endpoints

- a.** Safety will be evaluated by tabulation of adverse events (AEs), including any Serious Adverse Events (SAEs) within treatment groups. All AEs occurring during the study will be recorded. Descriptions of adverse events will include the date of onset, the date the adverse event ended, the severity of the adverse event, and the outcome. All reported adverse events will be summarized by the number of subjects reporting adverse events, body system, severity, seriousness, and relationship to study treatment.

3. Analysis of Other Endpoints

- a.** Other variables may be analyzed and presented descriptively. The methods to be used will include (but are not limited to) parametric and nonparametric analysis, means, standard deviations, frequency counts and graphs, as appropriate.
- b.** Video footage of patient experiences will be compiled at the end of the study. The compiled video footage will subsequently be watched and analyzed to further understand the experiences of atopic dermatitis patients, and how undergoing dupilumab treatment alters these patients' experiences and attitudes with their skin disease.

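### The videos are meant to run from before dupilumab to after it, but no recording is planned before the first dose and no prompt asks about the untreated state

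*Combined protocol and SAP*

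**What the plan says.** **Purpose.** Section 2 (Study Rationale) gives each patient a recording device to "document their experience from a pre-dupilumab state to a post-dupilumab state in the privacy of their own home". It adds: "It is best to have both human-interest stories in a narrative form before and after treatment", alongside the questionnaire results, and names payers and the general public as the people such stories reach.

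**Endpoint and analysis.** Section 5.2 lists evaluation of the videos as secondary endpoint 7. Section 14.2, under other endpoints, says the compiled footage will be watched and analysed to understand patients' experience and "how undergoing dupilumab treatment alters these patients' experiences and attitudes with their skin disease".

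**Procedure.** Section 9.1.11 states: "Patients will be given a video recording device at week 0". The topic list is handed over at the same visit. Each week, for some 5 to 10 minutes, patients then "record videos of themselves at home discussing their experience with the study drug and its impact on their skin and quality of life". Section 10.02 (Week 0) has the entry "9. Study drug injection" and, as item 11, "Sign out video recording device and instruct patients on proper use". Section 10.01 (Screening) contains no video step. Section 8.4 has doses at the Week 0 to Week 48 visits given at the study site, once that visit's assessments are done.

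**The concern.** The study is open-label and every subject receives dupilumab, so the only comparison it can make within its own data is before against after. The rationale promises that comparison for the videos, and the analysis text implies it. If nothing is recorded before the first dose, the 'before' half can only be a memory, given by someone who is already on treatment and has been handed topics that mostly concern the drug and its effects. Recall of that kind may be coloured by how the patient feels now. The gap cannot be repaired for a subject once that subject has been dosed. Footage later shown as a before-and-after record would be misdescribed to the audience Section 2 has in mind.

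**Working it through.** No formula applies and the plan gives no figure to reproduce. The check sets the sections side by side and counts.

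**1. Can a planned recording precede the first dose?**

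- Video steps before Week 0 (Section 10.01): 0.
- Device and topic list received: Week 0 (Sections 9.1.11 and 10.02).
- Place of recording: home (Sections 2 and 9.1.11).
- First dose: on site, at the Week 0 visit (Sections 8.3, 8.4 and 10.02).

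Suppose the device is handed over after the injection, as the item numbers 9 and 11 might suggest. The first home recording then follows the dose. Suppose instead that it is handed over before the injection. The patient is still in the clinic, is dosed there, and records at home afterwards. Both orders give the same count: 0 planned pre-dose recordings.

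**2. Do the prompts ask for the earlier state?** The eight topics in Section 9.1.11, classified by what they ask:

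| Prompt | Subject | Asks for pre-treatment state? |
|---|---|---|
| 1 | Any skin changes while on drug | No |
| 2 | The most important change while on drug | No; presupposes change |
| 3 | Goals for the medication | No; looks ahead |
| 4 | Effect of the skin changes on life | No; presupposes change |
| 5 | Any change in how the patient feels since starting | No |
| 6 | Overall experience on drug | No |
| 7 | Notable events while on drug | No |
| 8 | Anything else about eczema | No; open, so recall is possible |

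Prompts concerning the drug, or changes or goals on it: 5 (prompts 1, 2, 5, 6, 7) + 1 (prompt 4) + 1 (prompt 3) = 7 of 8. Open prompts: 1 of 8. Prompts asking the patient to describe skin or life before treatment: 0 of 8. The clearest case of presupposed change is prompt 2: "What is the most important change that you have experienced while using the study drug".

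**3. Are the other outcomes affected?** Section 10.02 schedules EASI, IGA, photography, WPAI, PGWB, DLQI, itch, pain and PSQI at Week 0, and Section 8.4 puts dosing after the visit's assessments. These have a Week 0 baseline. The videos do not.

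**4. Does Appendix 1 change the answer?** In the text available, the mark for video instruction falls in the first column. So do the first marks for on-site dosing and photography, which the body of the protocol places at Week 0. The columns appear to have shifted when the table was read, so this is not evidence that instruction takes place at Screening.

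**The case against.** The strongest reply is that endpoint 7 promises less than the rationale does. Endpoints 1, 2, 3, 5 and 6 in Section 5.2 are defined from baseline; endpoint 7 is not. Section 14.2 attaches no score, test or threshold to the footage, and a patient can say in retrospect how treatment changed things. The topic list is offered as a guide rather than a script, and prompt 8 leaves room for life before treatment. A clip made in the first days may also lie close to the untreated state; the documents give no figure from which to judge that.

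These points stand, and they limit the consequence. They do not supply the missing recording: recall on drug is not the documentation from before to after that Section 2 describes.

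Some stronger readings are tempting but not supported:

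- **That the Week 0 item order proves the device is issued after the injection.** The visit lists are not stated to be chronological. Section 10.01 lists eligibility checks ahead of consent, although consent must precede any testing. The finding rests on home recording and an on-site first dose, not on item numbers.
- **That every prompt is about time on drug, or that the list as a whole is leading.** Prompt 3 looks ahead and prompt 8 is open. Prompts 1 and 5 ask about any changes, which allows for none, and prompts 6 and 7 do not mention change. Only 2 and 4 clearly presuppose it.
- **That the gap can be sized as 52 weeks × 30 subjects = 1,560 clips with none at baseline.** Section 9.1.11 sets minutes per week, not clips, and 30 is a ceiling. Only the zero is informative.

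**Conclusion.** The inconsistency is real. Followed exactly, the plan yields no planned recording before the first dose from any subject, and no prompt that asks for the untreated state. Sections 2 and 14.2 therefore describe a comparison that Sections 9.1.11, 10.01 and 10.02 do not provide for.

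The consequence is narrow: one unscored, qualitative endpoint out of seven secondary endpoints. A reader might infer that endpoint 7 fails by its own definition, or that the study's quality-of-life conclusions lose their baseline. Neither follows. Endpoint 7 names no baseline comparison, and the PGWB primary endpoint and the scored secondary endpoints are measured at Week 0. The sample size is not affected either.

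The conclusion assumes that the Week 0 visit is a single attendance at which the first dose is given, and that recording takes place at home as written.

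**What to change.** Amend Sections 9.1.11, 10.01 and 10.02, and align Appendix 1:

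- Issue the device after consent at Screening, or once eligibility is confirmed, and require at least one video before the first dose, downloaded at Week 0 before the injection. The documents do not give the interval between Screening and Week 0, so one video is the safe minimum to ask for.
- If that is impractical, record one private clip on site at Week 0 before the injection. This departs from the home setting but preserves the baseline.
- Add neutral baseline prompts on current skin, sleep, mood, work and relationships that make no mention of the drug. The same prompts may be reused at later visits to give like-for-like accounts.

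The cost is a short wording change and a revised topic sheet. Devices would be out somewhat longer. Devices issued to subjects who then fail screening must be recovered and their footage deleted or otherwise dealt with, since Section 12.2 collects no CRF data on screen failures.

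If the sponsor prefers to leave the procedure alone, reword Sections 2 and 14.2 so that the videos are described as on-treatment narratives with recall of the earlier state. That also removes the inconsistency, at the price of the prospective 'before'.

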3 STUDY OBJECTIVES

3.1 Primary Objective

To evaluate the improvement in patient quality of life after 52 weeks of treatment with dupilumab using validated dermatologic and non-dermatologic psychometric instruments. The primary endpoint is the improvement in quality of life measured by change in Psychological General Well-Being scale (PGWB) at Week 16 from baseline.

